Appendix 3. Study Governance, Regulatory and Ethical Considerations

Informed Consent

The investigator is responsible for

- ensuring that the participant understands the nature of the study, the potential risks and benefits of participating in the study, and that his/her participation is voluntary.
- ensuring that informed consent is given by each participant or legal representative. This includes obtaining the appropriate signatures and dates on the ICF prior to the performance of any protocol procedures and prior to the administration of investigational product.
- answering any questions the participant may have throughout the study and sharing in a timely manner any new information that may be relevant to the participant's willingness to continue his or her participation in the study.
- providing a copy of the ICF to the participant or the participant's legal representative and retaining a copy on file.

Recruitment

Lilly or its designee is responsible for the central recruitment strategy for participants. Individual investigators may have additional local requirements or processes. Study-specific recruitment materials should be approved by Lilly.

Ethical Review

The investigator must give assurance that the ethical review board (ERB) was properly constituted and convened as required by the ICH guidelines and other applicable laws and regulations.

Documentation of ERB approval of the protocol and the ICF must be provided to Lilly before the study may begin at the CRU. Lilly or its representatives must approve the ICF before it is used at the CRU. All ICFs must be compliant with the ICH guideline on GCP.

The study site's ERB(s) should be provided with the following:

- study protocol and any amendments during the course of the study
- the current IB and updates during the course of the study
- ICF
- relevant site personnel curricula vitae

Regulatory Considerations

This study will be conducted in accordance with the protocol and with

1. consensus ethics principles derived from international ethics guidelines, including the Declaration of Helsinki and Council for International Organizations of Medical Sciences International Ethical Guidelines
2. applicable ICH GCP Guidelines
3. applicable laws and regulations

Some of the obligations of the sponsor will be assigned to a third-party organization.

Protocol Signatures

The sponsor's medical officer responsible will approve the protocol, confirming that, to the best of his or her knowledge, the protocol accurately describes the planned design and conduct of the study.

Final Report Signature

The sponsor's medical officer responsible and statistician will sign/approve the final clinical study report for this study, confirming that, to the best of his or her knowledge, the report accurately describes the conduct and results of the study.

Data Quality Assurance

To ensure accurate, complete, and reliable data, Lilly or its representatives will do the following:

- provide instructional materials to the study sites, as appropriate.
- provide training to instruct the investigators and study coordinators. This training will give instruction on the protocol, the completion of the CRFs, and study procedures.
- make periodic visits to the study site.
- be available for consultation and stay in contact with the study site personnel through mail, telephone, and/or fax.
- review and evaluate CRF data and/or use standard computer edits to detect errors in data collection.
- conduct a quality review of the database.

In addition, Lilly or its representatives will periodically check a sample of the participant data recorded against source documents at the study site. The study may be audited by Lilly and/or regulatory agencies at any time. Investigators will be given notice before an audit occurs.

The investigator will keep records of all original source data. This might include laboratory tests, medical records, and clinical notes. If requested, the investigator will provide the sponsor, applicable regulatory agencies, and applicable ERBs with direct access to the original source documents.

Data Collection Tools/Source Data

An EDC system will be used in this study. The site must define and retain all source records and must maintain a record of any data where source data are directly entered into the data capture system.

Data Protection

Data systems used for the study will have controls and requirements in accordance with local data protection law.

The purpose and use of participant personal information collected will be provided in a written document to the participant by the sponsor.

Study and Site Closure

Discontinuation of Study Sites

Study site participation may be discontinued if Lilly or its designee, the investigator, or the ERB of the study site judges it necessary for medical, safety, regulatory, or other reasons consistent with applicable laws, regulations, and GCP.

Discontinuation of the Study

The study will be discontinued if Lilly or its designee judges it necessary for medical, safety, regulatory, or other reasons consistent with applicable laws, regulations, and GCP.

Appendix 4. Hepatic Monitoring Tests for Treatment-Emergent Abnormality

Selected tests may be obtained in the event of a treatment-emergent hepatic abnormality and may be required in follow-up with patients in consultation with Lilly medical monitor.

Hepatic Monitoring Tests

Hepatic Hematology^a	Haptoglobin^a
Hemoglobin	
Hematocrit	Hepatic Coagulation^a
RBC	Prothrombin Time
WBC	Prothrombin Time, INR
Neutrophils	
Lymphocytes	Hepatic Serologies^{a,b}
Monocytes	Hepatitis A antibody, total
Eosinophils	Hepatitis A antibody, IgM
Basophils	Hepatitis B surface antigen
Platelets	Hepatitis B surface antibody
	Hepatitis B Core antibody
Hepatic Chemistry^a	Hepatitis C antibody
Total bilirubin	Hepatitis E antibody, IgG
Conjugated bilirubin	Hepatitis E antibody, IgM
Alkaline phosphatase	
ALT	Anti-nuclear antibody^a
AST	Alkaline Phosphatase Isoenzymes^a
GGT	Anti-smooth muscle antibody (or anti-actin antibody)^a
CPK	

Abbreviations: ALT = alanine aminotransferase; AST = aspartate aminotransferase; CPK = creatinine phosphokinase; GGT = gamma-glutamyl transferase; Ig = immunoglobulin; INR = international normalized ratio; RBC = red blood cells; WBC = white blood cells.

a Assayed by Lilly-designed or local laboratory.

b Reflex/confirmation dependent on regulatory requirements and/or testing availability

Appendix 5. Blood Sampling Summary

This table summarizes the approximate number of venipunctures and blood volumes for all blood sampling (screening, safety laboratories, and bioanalytical assays) during the study.

Protocol J2D-MC- CVAB Sampling Summary

Purpose	Blood Volume per Sample (mL)	Number of Blood Samples	Total Volume (mL)
Screening tests ^a	11.5	1	11.5
Clinical laboratory tests ^a	6.5	10	65
Pharmacokinetics	3	16	48
Total (rounded-up)			125

^a Additional samples may be drawn if needed for safety purposes.

Appendix 6. Protocol Amendment J2D-MC-CVAB(a) Summary

Protocol J2D-MC-CVAB has been amended in response to queries raised by Federal Agency for Medicines and Health Products (FAMHP), Belgium. The new protocol is indicated by Amendment (a), dated 15 Nov 2019, and will be used to conduct the study in place of any preceding version of the protocol.

The overall changes and rationale for the changes made to this protocol are as follows:

Section # and Name	Description of Change	Brief Rationale
6.1. Inclusion Criteria	Contraception language changed (Criterion 1.d.i) per 'Recommendations related to contraception and pregnancy testing in clinical trials of the Clinical Trial Facilitation Group (CTFG)'	Criterion updated in response to FAMHP query.

Revised Protocol Sections

Note: Deletions have been identified by ~~strikethroughs~~ or grayed out for figures.
Additions have been identified by the use of underscore.

6.1. Inclusion Criteria

1. Healthy female participants as determined by medical history and physical examination.
 - a. Female participants must be nonpregnant and not lactating, or of nonchildbearing potential (either surgically sterilized [e.g. tubal occlusion, hysterectomy, bilateral salpingectomy] or physiologically incapable of becoming pregnant, or postmenopausal with amenorrhea for at least 12 consecutive months)
 - b. Nonpregnancy will be confirmed for all female participants through a serum pregnancy test at screening, at (each) admission to the CRU and, at other time points specified in the Schedule of Activities (Section 2). Follicle-stimulating hormone will be tested at screening for all female participants.
 - c. Healthy female participants of child-bearing potential who have a fertile male sexual partner must be willing and able to practice effective contraception from screening visit \leq 28 days to 30 days after the final visit.

d. Sexually active participants must use a combination of 2 of the following methods of contraception, including so called 'barrier' methods:

- i. Hormonal contraceptive associated with inhibition of ovulation (oral, transdermal patches, vaginal or injectable)
- ii. Intrauterine device with or without hormones
- iii. Condom, diaphragm or cervical cap ('barrier' methods)

Contraceptive requirements do not apply for participants who are sexually abstinent or exclusively in same-sex relationships.

Leo Document ID = 36fbadb3-6a3d-466d-93b0-69a2e8274c2d

Approver: [REDACTED]

Approval Date & Time: 15-Nov-2019 15:45:35 GMT

Signature meaning: Approved

Approver: [REDACTED]

Approval Date & Time: 15-Nov-2019 16:37:06 GMT

Signature meaning: Approved

3.0 Introduction

This Statistical Analysis Plan (SAP) describes the statistical methods that will be used during the analysis and reporting of data collected under Eli Lilly and Company Protocol J2D-MC-CVAB(a).

This SAP should be read in conjunction with the study protocol and electronic case report form (eCRF). This version of the plan has been developed using the protocol dated 15-Nov-2019 (including all amendments up to this protocol date) and the final eCRF(s) dated 03-Jan-2020.

An approved and signed SAP is a requirement for database lock. An approved SAP is also required for unblinding of the study treatments.

This SAP only covers the results that will be processed by the PRA Early Development Services (EDS) Biostatistics Department.

PRA EDS will perform the pharmacokinetic (PK), pharmacodynamic (PD), and safety and tolerability evaluation.

This SAP supersedes the statistical considerations identified in the protocol; where considerations are substantially different, they will be so identified. Any post-hoc or unplanned analyses, or significant changes from the planned analysis in this SAP performed to provide results for inclusion in the clinical study report (CSR) but not included in this SAP, will be clearly identified in the CSR. Changes to planned analyses do not require an updated SAP but should be included in the CSR if significant.

4.0 Changes from Previous Version of Approved SAP

This is the first version of the SAP.

5.0 Study Objectives

5.1 Primary

To assess target engagement of TRPA1 after a single dose of LY3526318.

5.1.1 Primary Endpoint

Decrease in cinnamaldehyde (CA)-induced dermal blood flow (DBF) relative to placebo measured by laser Doppler Imaging (LDI) at 3 hours post-dose.

5.2 Secondary

- To evaluate the safety and tolerability in healthy females following single oral doses of LY3526318.
- To assess target engagement of TRPA1 after a single dose of LY3526318 using Laser Speckle Contrast Imaging (LSCI), an alternate imaging method.
- To assess the pharmacokinetics of LY3526318 following single oral doses of LY3526318.

5.2.1 Secondary Endpoints

- Treatment-emergent (TE) adverse events (AE), serious AEs.
- Decrease in CA-induced DBF relative to placebo measured by LSCI at 3 hours post-dose.
- Summary of LY3526318 plasma concentrations by dose and time point.

5.3 Exploratory

- To assess target engagement of TRPA1 after a single dose of LY3526318.
- To explore the relationship between LY3526318 plasma concentration and DBF in healthy females following a single oral LY3526318 dose.

5.3.1 Exploratory Endpoints

- Decrease in CA-induced DBF relative to placebo measured by LDI at 24 hours post-dose.
- Decrease in CA-induced DBF relative to placebo measured by LSCI at 24 hours post-dose.
- LY3526318 plasma concentrations.
- DBF.

5.4 Study Hypothesis

The null hypothesis H_0 is that there is no decrease in CA-induced DBF relative to placebo measured by laser Doppler Imaging (LDI) at 3 hours post-dose at an α level of (0.05/3), one-sided. Bonferroni adjustment is used to account for the three comparisons (dose levels) versus placebo.

If the null hypothesis is rejected for any of the dose levels, the alternative hypothesis, i.e. there is a decrease for this dose level, will be accepted.

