6.1 Sample Size Considerations

The sample size is justified based on the statistical power to meet the primary endpoint of DBF measurements from LDI assay at t_{max} . The power calculation used 10% CA-induced absolute DBF in comparison between LY3526318 and placebo arms. For a 20% reduction in DBF (assuming mean observed placebo DBF of 444.3 arbitrary perfusion units (PU) with standard deviation (SD) of 55.1 PU) and a significance level of 0.05, a paired t-test with 16 patients results in 98% power to reject the null hypothesis. Incorporating a Bonferroni adjustment to account for multiplicity (changing the significance level to 0.05/3) lowers the power slightly to 96%.

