9.4.3 Hypothesis Testing

Significance testing will be 1-sided at the significance level of 0.05/3 for the primary statistical analysis.

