17.2.2 Statistical Analysis

An analysis of variance (ANOVA) will be performed on the percentage change (pre- to post-CA) at time points 3 h and 24 h post-dose using PROC MIXED in SAS. The percentage change will be used untransformed in the analysis. The model will include fixed effects for treatment, period, sequence, time and treatment*time interaction and a random effect for subject within sequence. The analysis will be done for each, method and CA concentration separately. From this model the least-squares means (LSMeans) for each treatment (including placebo) and the difference of the LSMeans for each of the active treatments with placebo at 3 h and at 24 h post-dose and the corresponding P value will be estimated for each method and CA concentration.

In the summary of the statistical analysis, it will be indicated that the result for LDI, 3 hours post-dose is the primary end point.

In SAS code:

```

proc mixed data=dbf;
  by CAconc method;
  class subject trtan time           period seq;
  model pchg = trtan time trtan*time period seq;
  random subject(seq);
  lsmeans trtan*time ;
  /*estimates*/
run;
quit;

```

For each of the active dose levels and CA concentrations, a decrease relative to placebo of the percentage change (pre- to post-CA) with a P value below (0.05/3) will be considered statistically significant.

Additionally, the same model (with fixed effects for treatment, period, sequence, time and treatment*time interaction and a random effect for subject within sequence) will be applied to the absolute values for each method and CA concentration separately, using data from all time points (i.e. pre study drug, 3 h pre- and post-CA, 24 h pre- and post-CA). From this model, using the absolute values, LSMeans and the differences with 90% CI and P-value will be estimated for each method and CA concentration for the following comparisons:

#	LSMean (absolute value) of	Compared with LSMean (absolute value) of
1	D1 post-CA at 3 h	Placebo post-CA at 3 h
2	D2 post-CA at 3 h	Placebo post-CA at 3 h
3	D3 post-CA at 3 h	Placebo post-CA at 3 h
4	D1 post-CA at 24 h	Placebo post-CA at 24 h
5	D2 post-CA at 24 h	Placebo post-CA at 24 h
6	D3 post-CA at 24 h	Placebo post-CA at 24 h
7	Placebo pre-CA at 3 h	Placebo pre study drug at 0 h
8	D1 pre-CA at 3 h	D1 pre study drug at 0 h
9	D2 pre-CA at 3 h	D2 pre study drug at 0 h
10	D3 pre-CA at 3 h	D3 pre study drug at 0 h
11	Placebo pre-CA at 24 h	Placebo pre study drug at 0 h

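### Flat Bonferroni at one-sided 0.05/3 for the three dose comparisons is valid but less efficient than Holm; the gain is small at the planned effect and larger only if some doses work less well

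*SAP*

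**What the plan says.** SAP 5.4 sets the primary null hypothesis "at an α level of (0.05/3), one-sided" and explains that "Bonferroni adjustment is used to account for the three comparisons (dose levels) versus placebo". Conclusions are drawn dose by dose: a rejection at any one dose leads to a claim of reduced flow at that dose.

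SAP 9.4.3 repeats the threshold: "Significance testing will be 1-sided at the significance level of 0.05/3 for the primary statistical analysis". SAP 17.2.2 applies it to each active dose and each CA concentration: "a decrease relative to placebo of the percentage change (pre- to post-CA) with a P value below (0.05/3) will be considered statistically significant". No step-down, fixed sequence or other ordering is described, and no reason is given for the flat rule.

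Protocol 10.1 and SAP 6.1 disclose the cost of the adjustment. For a 20% reduction and 16 participants, power falls from 98% at 0.05 to 96% at 0.05/3. That calculation uses absolute flow after 10% CA.

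For the percentage-change model, SAP 17.2.2 lists least-squares means, differences and P values. A 90% confidence interval is named only for the model on absolute values.

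**The concern.** The flat rule judges each dose as though nothing had been learned from the other two. Once one dose has been rejected at 0.05/3, at most two true null hypotheses can remain, so the next P value can be compared with 0.05/2 and the last with 0.05 without exceeding 5% across the family.

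The plan wants a verdict for each dose, so what is at stake is power for the doses with the second and third smallest P values. Those are the lower doses only if the effect rises with dose. The usual reason to keep plain Bonferroni, simple simultaneous confidence intervals, does not apply here, because none are planned for the primary analysis.

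**Working it through.** **Inputs from the documents.** Placebo mean 444.3 PU, SD 55.1 PU, 20% reduction, n = 16 (SAP 6.1); 0.05/3 one-sided (SAP 5.4, 9.4.3); every participant receives placebo and all three doses (SAP 6.0). The SD of the paired difference and the within-subject correlation are not given.

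**The plan's own figure.** δ = 0.20 × 444.3 = 88.86 PU. With zero correlation (assumed), the SD of the difference is 55.1 × √2 = 77.92. The noncentrality is 88.86 / (77.92/√16) = 4.56 on 15 df.

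- Two-sided paired t-test: 98.9% at 0.05 and 95.7% at 0.05/3, close to the stated 98% and 96%.
- One-sided, as the SAP tests: 99.7% and 98.1%.
- With correlation 0.5 the SD of the difference is 55.1 and power is at least 99.96% throughout, which does not match.

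Zero correlation is therefore the reading that comes closest to the plan's figures.

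**Why Holm cannot lose a dose.** If Bonferroni rejects k doses, the k smallest P values all lie below 0.05/3. They then also pass Holm's first k thresholds (0.0167, 0.025, 0.05), which are equal or looser.

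**Why Holm holds 5%.** With m true nulls, Holm's first false rejection needs a true-null P value of at most 0.05/m. The chance of that is at most m × 0.05/m = 0.05, whatever the dependence.

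**Power.** Simulated balanced crossovers (200,000 to 300,000 per scenario) with one-sided tests and a shared placebo. The SE of a treatment mean is 55.1/√16 = 13.78 PU, and the residual df are 63 − 15 (participants) − 3 (periods) − 3 (treatments) = 42. The dose responses other than 20/20/20 are assumptions.

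| True reduction | Quantity | Bonferroni | Holm |
|---|---|---|---|
| 20/20/20% | each dose | 99.0% | 99.7% |
| 20/20/20% | all three | 97.3% | 99.3% |
| 10/15/20% | 10% dose | 54% | 71% |
| 10/15/20% | 15% dose | 88% | 93% |
| 10/15/20% | all three | 52% | 71% |
| 5/10/20% | 5% dose | 15% | 27% |
| 5/10/20% | 10% dose | 53% | 62% |

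Paired t-tests on 15 df (100,000 runs) give the same pattern:

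- 20/20/20%, one-sided: each dose 98.1% to 99.5%, all three 95.1% to 99.0%.
- 20/20/20%, two-sided: each dose 95.7% to 98.5%.
- 10/15/20%, one-sided: weakest dose 49% to 69%, middle dose 85% to 91%.

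In every scenario the power to reject at least one dose was identical under the two methods, and no Bonferroni rejection was lost.

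**False rejections (42 df).**

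| True reduction | Quantity | Bonferroni | Holm |
|---|---|---|---|
| 0/0/0% | any false rejection | 4.2% | 4.2% |
| 0/0/20% | any false rejection | 3.1% | 4.5% |
| 0/20/20% | inert dose declared active | 1.7% | 5.0% |

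The last row also follows directly. When the two active doses are nearly always rejected, the inert dose is tested at 0.05 instead of 0.05/3 = 0.0167.

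**Sensitivity to the SD.** With SD 80 PU (assumed) and all doses at 20%, per-dose power goes from 82% to 89%, and power for all three from 65% to 82%.

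**The case against.** Flat Bonferroni is prespecified, controls the error rate across the doses, and has a disclosed power cost. At the only effect the documents plan for, Holm adds about 1 to 3 points per dose. The larger gains come from dose responses that appear nowhere in the documents; protocol 5.5 expects the chosen doses to lie in the range that engages the target. The simulation uses absolute flow, whereas the primary test is on percentage change, for which no SD is given. The SAP also fits 3 h and 24 h together, so 42 df is not the planned residual df. No dose-ranging objective is stated, and exposure-response is to be explored through concentrations. All of this stands, and it limits the weight of the point.

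It does not remove the point. Doses may span 10 to 100 mg (protocol 7.1), and nothing in the documents says they share one effect. The SAP commits to a conclusion for each dose.

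Three stronger readings are tempting, and the documents do not support them:

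- **That the flat rule wastes power at no return.** It does buy something: an inert dose alongside two active ones is falsely declared about 1.7% of the time rather than 5.0%.
- **That the primary objective is underpowered or its error rate inflated.** Power to show engagement at one or more doses is the same under both rules, and the flat rule is, if anything, conservative.
- **That either rule protects the whole primary analysis at 5%.** SAP 17.2.2 applies 0.05/3 separately for each CA concentration, so the protection covers only three doses within one concentration.

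**Conclusion.** The point holds as one of efficiency, not of error. Holm gives the same family-wise guarantee with no added assumption and cannot reject fewer doses. At the planned 20% effect for every dose the benefit is small: 1 to 3 points per dose, and for all three about 97% to 99% on 42 df or 95% to 99% with one-sided paired t-tests. It becomes material, roughly 17 points for the weakest dose under 10/15/20% (71 − 54), only if some doses have smaller effects or variability is larger than planned. Both are assumptions, and the size of the gain on the percentage-change endpoint is unknown. Low priority.

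**What to change.** In SAP 5.4, 9.4.3 and 17.2.2, for the primary analysis of percentage change by LDI at 3 h:

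- Name the CA concentration that carries the primary test. The power calculation used 10%.
- State that the family is the three dose-placebo comparisons within that concentration.
- Order the three one-sided P values, compare the smallest with 0.05/3, the next with 0.05/2 and the largest with 0.05, and stop at the first that fails. State the sidedness in 17.2.2 too, which does not repeat it.

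The cost is SAP wording and a few lines of code; design, sample size and data collection are untouched. Two downsides should be accepted openly: the higher false-rejection chance for an inert dose when the others work, and the fact that simple Bonferroni intervals, if later added, would not match the decisions exactly. The change must be made before unblinding, because a switch of decision rule after the P values are known would not be credible.
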